In those with posttraumatic stress disorder (PTSD), trauma-related nightmares are a hallmark re-experiencing symptom and a common and severe source of distress often resulting in re-traumatization due to the lack of insight afforded by wakefulness. Proposed research will examine whether such nightmares might serve as targets for imaginal exposure during prolonged exposure therapy (PE), a first line treatment for PTSD. PE produces significant PTSD symptom reduction. However, approximately 30% of patients prematurely drop out from PE treatment and most still meet diagnostic criteria for PTSD at end of treatment. Thus, means for increasing the efficacy of PE are important areas of investigation. Fear extinction learning and memory are the neurocognitive underpinnings of PE. Because increased physiological arousal during PE can aid in extinction learning, recall of trauma-related nightmares might serve as an effective target for PE because of their greater immediacy and salience relative to the more temporally distant traumatic event. Our research group has developed standardized script-driven imagery (SDI) procedures whereby the degree of psychophysiological arousal induced by recollection of the traumatic event that precipitated posttraumatic symptoms (index trauma) can be assessed in those with PTSD. A canonical variable for physiological reactivity to SDI (SDI-PR) is derived from skin conductance (SC), facial electromyography (EMG) and electrocardiography (ECG) and has served as a unitary, objective measure capable of distinguishing those with versus without clinician-diagnosed PTSD. Members of our team have also developed a novel ambulatory device, the NINscan, that can record SC, EMG and ECG along with simultaneous functional near-infrared spectroscopic (fNIRS) imaging of the lateral prefrontal cortex (LPFC). fNIRS yields concentrations of oxygenated ( $O_2Hb$ ) and deoxygenated (HHb) hemoglobin that can be used to assess cortical activation. Specific areas of the LPFC have been shown to activate and/or deactivate during SDI of an index trauma in persons with PTSD. Notably, the LPFC includes the right inferior frontal gyrus (rIFG), a region shown to play a prominent role in inhibiting unwanted behavior and cognition, in which reduced activation accompanies reduced inhibitory performance in persons with PTSD, compared to controls. In participants with PTSD and trauma-related nightmares, proposed research will compare psychophysiological responses and LPFC activation between SDI of a recent trauma-related nightmare versus SDI of the index trauma. During nights over a 2-week period, participants will audio-record timestamped nightmare reports following all nightmare-induced awakenings. During two to four such nights, ambulatory polysomnography (PSG) will allow analysis of sleep physiology immediately preceding nightmare awakenings. A trauma-related nightmare report having sufficient length, clarity and resemblance to the index trauma will be selected and recorded as a script for SDI. The overarching goal of the proposed research will be to compare within-subject similarities and differences in brain and autonomic activation between imaginal replay of a trauma-related nightmare versus imaginal replay of the index trauma to determine the relative degree to which each evokes autonomic and frontocortical activations.

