
# SPECIFIC AIMS

Specific Aim 1: Optimize standard operating procedures for using the NINscan device in our established SDI protocol as a flexible and portable alternative to previously employed laboratory-based hardware that lacked simultaneous fNIRS capacity."

*Hypothesis* 1: "NINscan will be easily optimized for SDI assessment in the MGH psychophysiology laboratory including event marking and systems for viewing incoming data in real time."

Specific Aim 2: Compare autonomic reactivity (SDI-PR) and fNIRS activation of the LPFC during SDI of the index trauma script and a trauma-related nightmare script.

*Hypothesis 2:* SDI-PR and LPFC activations during SDI of the trauma-nightmare script will exceed activations during SDI of the index-trauma.

Exploratory Aim 1: Determine whether the sleep stage immediately prior to traumanightmare awakenings and the trauma-nightmare content determine which individuals respond more to trauma-nightmare SDI or show a greater response to index-trauma SDI.

*Exploratory hypothesis 1A:* Individuals for whom the nightmare used to create their traumanightmare script was preceded, before awakening, by REM versus NREM sleep, will show greater SDI-PR and rIFG HbD responses to the trauma-nightmare script than to the indextrauma script.

*Exploratory hypothesis 1B*: Individuals for whom the trauma-nightmare script is judged most similar to the index trauma and/or the most severely stressful by 3 independent judges will show

greater SDI-PR and rIFG HbD responses to the nightmare script, compared to the index-trauma script.

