# INCLUSION/EXCLUSION CRITERIA

# Phase 1

- 1. Age 18-60 years
- 2. Normal or corrected to normal visual acuity, normal hearing
- 3. Index event that meets DSM-5 PTSD stressor criterion A, *viz.* "The person was exposed to death, threatened death, actual or threatened serious injury, or actual or threatened sexual violence" by direct exposure, witnessing in person, or having a close relative or friend exposed to violent or accidental actual or threatened death.
- 4. Self-report of at least 2 nightmares per week related to the index trauma. The trauma nightmares must contain veridical (vs., symbolic, interpreted, etc.) content that is reminiscent of the index trauma.
- 5. Individuals who meet criteria for at least three of the four DSM-5 criterion categories.

# Phases 2 & 3

During the 2-week monitoring period (Phase 1), at least 4 recorded nightmares related to the index trauma with at least one suitable for creating a script for SDI.

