# Retention

Any withdrawals from the study will be replaced such that a total of 50 study completers will be achieved. During the 14-day Phase 1 sleep-recording period, research staff will be in frequent contact with each participant. Participants will come to the Sleep and Anxiety Disorders lab to be instrumented for recordings on each evening prior to recording nights and they will also arrange with staff to return the equipment (usually on the following day). At each evening visit, participants will also meet with the PI or other clinical staff to complete the Columbia-Suicide Severity Rating Scale (C-SSRS) via Zoom at which time they will be asked of any difficulties they have encountered with the study procedures and will be able to solve such problems with staff assistance. As in all of our studies, participants are encouraged to call the PI 24/7 with any concerns. For additional incentive to complete all study assessments, we offer a \$100 bonus for completing the entire protocol.

When a candidate subject responds to an advertisement, they will be instructed to leave a phone number but remain anonymous until accepted into the first phase of the study. They will then be called and given a detailed description of the study. If they continue to be interested in participation, a phone screening will be conducted by one of the study investigators by a trained research assistant. Those not meeting inclusion/exclusion criteria or who choose not to participate will, therefore, remain anonymous. In the phone screening, major inclusion criteria will be confirmed and exclusion criteria ruled out based upon the candidate participant's self-report. Candidate participants' names, addresses and email addresses will be obtained if (and only if) they are determined to meet these initial inclusion/exclusion criteria and wish to participate.

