Structured Clinical Interview for DSM-5, Research Version (SCID-5-RV) and the Clinical Interview for DSM-5 Sleep Disorders Module (SCISD), and screened for suicidality using the Columbia-Suicide Severity Rating Scale (C-SSRS). They will then be screened for PTSD symptomatology with the CAPS-5, PCL-5, Childhood Trauma Questionnaire (CTQ), Trauma History Questionnaire (THQ), Life Events Checklist for DSM-5 (LEC-5) and Peri-traumatic Distress Inventory (PDI). Phase 1 inclusion criteria will be a SCID-5-RV-based diagnosis of PTSD and self-report of at least 2 nightmares per week related to a specific "index trauma" that contains veridical content reminiscent of the index trauma. Phase 2 and 3 criteria will be at least 4 audio-recorded, time-stamped nightmares related to the index trauma during the 14 nights of Phase 1 with at least one that is suitable for SDI.

**Phase 1:** Participants accepted to Phase 1 will give an audio-recorded narrative of the index trauma for later SDI. They will then receive an actiwatch, a voice-activated, time-stamping digital audio-recorder, a list of bodily sensations that they might experience during nightmares, and copies of the Evening/Morning Sleep Questionnaire (EMSQ) diary. All nightmares resulting in awakenings will be recorded at the time of awakening. Participants will be instructed to depress the actiwatch event marker when they awaken and when they complete recording and to estimate the subjective duration of the nightmare. Audio-recorded nightmare reports will be compared, by study staff, with the audio-recorded narrative account of the index trauma. Participants will also complete a battery of questionnaires, remotely, and two to four nights of ambulatory PSG using the Somte-PSG ambulatory recorder (Compumedics USA, Inc., Charlotte, NC). The first night will screen for sleep disorders and acclimate participants to PSG. Participants who do not record 4+ TRNs one of which is suitable for SDI during Phase 1 will be debriefed, paid for portions of the study completed and discharged.

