**Phase 2:** Participants will undergo a structural T1 MPRAGE MRI scan. This will be used along with the BrainSight Frameless Stereotactic System (Rogue Research, Inc., Montreal, CN) to localize fNIRS optodes at 8 bilateral regions of interest (ROIs) (4 per hemisphere) including the frontopolar cortex (BA 10), as well as superior (BA 9), middle (BA 46) and inferior (BA 47) frontal gyri.

**Phase 3:** When we capture a suitable nightmare from a participant, the recorded nightmare report will be transcribed and audio-recorded by an investigator as a TRN script following our standard procedures. Participants will then come to the laboratory and complete 2 SDI sessions with NINscan monitoring, one of which will use the script derived from the TRN and the other the script derived from the index trauma. Presentation order of the scripts derived from the TRN and from the index trauma will be counterbalanced across participants. Because PTSD symptomatology and extinction memory may vary with the menstrual cycle, female participants not on oral contraceptives will undergo SDI during the early follicular phase of their cycle.

**Script Driven Imagery**: Adapting standardized SDI protocols, scripts will be created from audio-recorded accounts of the index trauma about which a participant's TRNs represent a re-experiencing. The audio-recorded report and list of bodily sensations experienced from an awakening during Phase 1 will provide material for the nightmare script. Account of a second personalized stressful event unrelated to the index traumatic event will be similarly recorded as well as one recording each of a recalled positive and emotionally neutral experience. These accounts will be transcribed and the subject will clarify and expand on details as necessary. Scripts approximately 30 sec in duration will then be composed and recorded by experienced staff, portraying each experience in the second person, present tense. Six 30-sec standard generic scripts of both neutral and emotional situations (2 each of neutral, fearful and positive

experiences) will also be recorded. Script recordings will be played to participants through headphones as they vividly imagine each event and physiological data are continuously sampled.

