**Power analysis:** For the primary outcome in Aim 2, we will compare physiological response and fNIRS in the rLIFC between scripts for the index trauma and the associated nightmare in each of 40 subjects completing the study (i.e., dropouts will be replaced). Based on a paired t-test at the 0.05/2 two-tailed significance level (adjusting for the two outcome measures), we will have 80% power to detect an effect size of d=0.50. In order to power the hypothesis in Exploratory Aim 1, we first assume that each of 50 subjects have one nightmare and that 60% of these nightmares will occur during REM sleep. For this situation, we will have 80% power to detect whether the probability of having greater SDI-PR or rIFG HbD response to the traumanightmare, compared to the index-trauma script is 0.70 or greater for patients who had nightmares during REM sleep, and 0.30 or less for those whose nightmares were not during REM sleep, based on Fisher's exact test, at the 0.05 two-tailed significance level.

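### Power for Exploratory Hypothesis 1A assumes a sleep stage for all 50 scripted nightmares, but nothing ties the script to a PSG night

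*Combined protocol and SAP*

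**What the plan says.** In the combined protocol and SAP, Specific Aims defines the 1A comparison as "Individuals for whom the nightmare used to create their traumanightmare script was preceded, before awakening, by REM versus NREM sleep". The stage must therefore belong to the scripted nightmare itself. Under Statistical analyses, the 1A logistic model enters REM as 0/1, with no category or rule for an unknown stage.

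The Power analysis paragraph states: "we first assume that each of 50 subjects have one nightmare and that 60% of these nightmares will occur during REM sleep". It then claims 80% power for response probabilities of 0.70 (REM) and 0.30 (not REM), by Fisher's exact test at two-sided 0.05.

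On where the stage comes from:
- The opening overview says "During two to four such nights, ambulatory polysomnography (PSG) will allow analysis of sleep physiology immediately preceding nightmare awakenings".
- The Phase 1 text adds "The first night will screen for sleep disorders and acclimate participants to PSG".
- Retention says "Participants will come to the Sleep and Anxiety Disorders lab to be instrumented for recordings on each evening prior to recording nights".
- Actigraphy, worn throughout, separates only sleep from wake.

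On where the script comes from:
- The opening overview says "A trauma-related nightmare report having sufficient length, clarity and resemblance to the index trauma will be selected and recorded as a script for SDI".
- Script Driven Imagery says "The audio-recorded report and list of bodily sensations experienced from an awakening during Phase 1 will provide material for the nightmare script".
- Entry to Phases 2 and 3 requires "at least 4 recorded nightmares related to the index trauma with at least one suitable for creating a script for SDI".

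Recruitment and Retention provide for replacing withdrawals, not completers whose script nightmare has no stage.

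**The concern.** The script is chosen on the quality of the report, from any night of Phase 1. The stage exists only for nightmares on PSG nights, and those nights are fixed when the participant is instrumented, before anyone knows whether a nightmare will occur. Nothing in the plan makes the two coincide. Nor does it say whether a nightmare on the diagnostic night can supply the stage, or what happens in 1A to a completer whose script nightmare was not staged.

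Hypothesis 1A may therefore be analysable in clearly fewer than 50 completers, at less than the stated power. A null result could then reflect too few staged scripts rather than no REM association. Without a written rule, who enters the 1A analysis also depends on ad hoc choices of script.

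**Working it through.** **Inputs from the protocol.** 50 completers; 60% REM, so 30 REM and 20 not REM; 0.70 versus 0.30; Fisher's exact test, two-sided 0.05 (Power analysis). Two to four PSG nights, the first for screening and acclimation (Phase 1 text). A 14-night window with at least four index-related nightmares, at least one suitable (Inclusion/Exclusion Criteria, Screening).

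**Assumptions not in the protocol.** Suitable nightmares fall on distinct nights spread evenly over the 14. The number suitable per participant, k, is varied. The 60% REM share holds among staged nightmares.

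**Step 1: the plan's own figure.** Exact power is the sum, over all tables with Fisher p ≤ 0.05, of Bin(x; n₁, 0.70) × Bin(y; n₂, 0.30). With n₁ = 30 and n₂ = 20 this is 79.5%. The stated 80% is reproduced for 50 staged scripts.

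**Step 2: expected number staged.** With m PSG nights, and a PSG-night nightmare used whenever one of the k suitable ones falls there,

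staged = 50 × [1 − C(14−m, k) / C(14, k)].

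For example, m = 2 and k = 4 gives 50 × [1 − C(12,4)/C(14,4)] = 50 × (1 − 495/1001) = 25.3. With k = 1 the formula reduces to 50 × m/14, which also describes selection that ignores PSG. The m = 1 column applies if only two PSG nights are run and the diagnostic night does not count.

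| Suitable nightmares (k) | m = 1 | m = 2 | m = 3 | m = 4 |
|---|---|---|---|---|
| 1, or selection ignores PSG | 3.6 | 7.1 | 10.7 | 14.3 |
| 2 | 7.1 | 13.7 | 19.8 | 25.3 |
| 4 | 14.3 | 25.3 | 33.5 | 39.5 |
| 8 | 28.6 | 41.8 | 47.3 | 49.3 |

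**Step 3: power at those numbers** (0.70 versus 0.30, same enumeration as Step 1).

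| Staged (REM/not REM) | Power |
|---|---|
| 4 (2/2) | 0% |
| 7 (4/3) | 8.3% |
| 11 (7/4) | 11.3% |
| 14 (8/6) | 19.1% |
| 20 (12/8) | 29.8% |
| 25 (15/10) | 47.8% |
| 29 (17/12) | 48.5% |
| 34 (20/14) | 58.1% |
| 40 (24/16) | 62.5% |
| 42 (25/17) | 65.3% |
| 47 (28/19) | 75.8% |
| 49 (29/20) | 78.2% |
| 50 (30/20) | 79.5% |

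**Step 4: ranges for two to four PSG nights.** Figures in brackets leave out the diagnostic night (one to three nights).
- Selection ignores PSG, or one suitable: 7–14 staged, power 8–19% [4–11, 0–11%].
- PSG night always preferred, two suitable: 14–25 staged, 19–48% [7–20, 8–30%].
- PSG night always preferred, four suitable: 25–40 staged, 48–63% [14–34, 19–58%].
- PSG night always preferred, eight suitable: 42–49 staged, 65–78% [29–47, 48–76%].

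**Step 5: detectable difference.** The smallest contrast 0.5 + d versus 0.5 − d with at least 80% power, in steps of 0.005 in d, is 0.705 vs 0.295 with 50 staged, 0.74 vs 0.26 with 40, 0.78 vs 0.22 with 25, and 0.885 vs 0.115 with 14.

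**The case against.** The opening overview puts nightmare recording, PSG and script selection in consecutive sentences, and 1A takes it for granted that the scripted nightmare has a stage. A reader could infer that PSG-night nightmares are meant to be used. That is plausible, but it is not written anywhere, and the rows that assume a PSG night is always preferred still fall short of 80%.

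The lowest rows may be pessimistic. Participants report at least two index-related nightmares a week and are sampled for likely usable reports, so four to eight suitable nightmares may be more realistic than one. This is fair. The protocol does not fix the number, so no row is established and the span reflects assumptions. The bracketed figures carry least weight: under PSG measures, the diagnostic night adds channels to the ordinary montage, so it could be staged, and no text excludes its nightmares. The 0% arises only because a 2-versus-2 table cannot reach significance.

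PSG nights might be added when none has yet caught a nightmare, which would make the two-night figures too low. The plan does not say so, and the cap of four nights keeps the m = 4 column as the ceiling under these assumptions.

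The power statement is openly conditional, and the aim is exploratory. Both are true, and they limit the severity. A stated power should still rest on a condition that the design can be expected to meet. Finally, restricting 1A to staged participants is largely what the model would do by default; writing it down mainly ensures that the number is reported.

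**Conclusion.** The concern holds. The 80% is arithmetically correct for 50 staged scripts, but the plan contains no rule that would produce 50. If nightmares are spread evenly and 60% are REM, power lies between 8% and 78% for two to four PSG nights. The result depends on how scripts are selected and how many nightmares are suitable; only eight suitable nightmares with four PSG nights comes close to the stated figure. The exact number staged cannot be derived from the documents. The consequence is confined to Exploratory Hypothesis 1A; Hypothesis 2 needs no sleep stage. It should be fixed, because the remedy is cheap and changes what 1A can conclude.

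**What to change.** 1. Add to the script-selection rule: among nightmares that meet the existing suitability criteria and are of comparable quality, use one recorded on a PSG night. Staff choosing the script should know whether PSG was running but not the stage.
2. State whether a nightmare on the diagnostic night may supply the stage.
3. State that 1A is limited to participants whose script nightmare has a PSG stage, and report that number. All others stay in Hypothesis 2.
4. Replace the single 80% statement by power, or the detectable difference, over a range of staged scripts (for example 14, 25, 40 and 50), with the assumptions stated.

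The cost is protocol wording and a less favourable stated power for an exploratory aim, with no extra PSG nights or participants. The chosen report also feeds Hypothesis 2, so the preference could occasionally bring in a less vivid or less closely matching nightmare. The comparable-quality condition limits this, but the rule then helps only participants with two or more suitable nightmares.

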# POTENTIAL RISKS AND PROTECTION FROM RISKS

# Risks of self-report during clinical screening, completing questionnaires and recording nightmares:

Participants may feel uncomfortable or embarrassed revealing psychological information during clinical interviews and when completing questionnaires. Interviews and questionnaires may also induce negative emotional reactions due to the reactivation of trauma-related memories. For the same reason, dictating dream reports following awakenings from nightmares may induce or

exacerbate trauma-related negative emotional reactions. The protections from these risks that we implement are detailed below.

## Risks from script-driven imagery (SDI) procedures:

Risks from the SDI procedure primarily include negative emotional reactions to the reactivation of trauma-related memories. There is a chance that recalling one's traumatic memories could worsen PTSD symptoms. However, we regard this as unlikely for two reasons. First, subjects with PTSD repeatedly experience traumatic memory reactivations as a feature of the disorder. Second, we have reactivated traumatic memories in hundreds of PTSD subjects during more than 30 years' experience with the script preparation procedure and have found few instances of symptomatic exacerbation. The protections from these risks that we implement are detailed below.

## **Risks from NIRS and NINscan monitoring:**

NIRS is an investigational tool in regular use for over 40 years. Although no adverse effects have been reported, it is possible that effects not yet reported may occur. If lasers like those in the device are shone directly into the eye, eye injury could potentially occur. NIRS monitoring requires coupling sensors to the skin on the scalp. This is achieved by fastening the sensors to a pad or cap, placing it over the head, and holding it in place with a head or chin strap. Positioning the sensors may require parting the hair and will require making secure contact with the skin. It is possible that skin irritation could occur beneath sensors. The study team has received extensive training on the psychophysiological procedures and this will minimize discomfort from the application of the electrodes.

